## **2.4 Secondary endpoints**

### **2.4.1 Supportive secondary endpoints**

#### **2.4.1.1 Efficacy endpoints**

##### **Other endpoints derived from the mixed meal tolerance test**

The other endpoints based on the mixed meal tolerance test will be derived from the individual C-peptide concentration-time curves and from the individual plasma glucose concentration-time curves. The AUC endpoints will be derived using the same approach as described for the primary endpoint. The  $C_{\max}$  endpoints will be derived as the ratio between the  $C_{\max}$  at the relevant time points.

The endpoints will be analysed using a similar model as applied for the primary endpoint except that the corresponding value at baseline will be included as a covariate.

The endpoints will be summarised using descriptive statistics and presented graphically. The C-peptide concentration-time curves and the plasma glucose concentration-time curves will be presented graphically.

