### 1.1.2.2 Supportive secondary endpoints

#### Supportive secondary efficacy endpoints

- $AUC_{0-4h}$  for MMTT stimulated C-peptide concentration time curve at week 80 relative to baseline\*
- $AUC_{0-2h}$  for MMTT stimulated C-peptide concentration time curve at week 54 and week 80 relative to baseline\*
- Maximum MMTT stimulated C-peptide concentration ( $C_{max, C-peptide}$ ) at week 54 and week 80 relative to baseline\*
- $AUC_{0-4h}$  for MMTT stimulated plasma glucose concentration time curve at week 54 and week 80 relative to baseline
- $AUC_{0-2h}$  for MMTT stimulated plasma glucose concentration time curve at week 54 and week 80 relative to baseline
- Maximum MMTT stimulated plasma glucose concentration ( $C_{max, glucose}$ ) week 54 and week 80 relative to baseline
- Change in total daily insulin dose in units per kg (three day average) from baseline to week 54 and week 80\*
- Change in number of insulin injections per day (three day average) from baseline to week 54 and week 80
- Number of weeks off bolus insulin from baseline to week 54 and week 80
- Change in  $HbA_{1c}$  from baseline to week 54 and week 80\*
- Change in fasting plasma glucose from baseline to week 54 and week 80\*
- Change in fasting C-peptide from baseline to week 54 and week 80\*
- Change in fasting glucagon from baseline to week 54 and week 80
- 7-point self-measured plasma glucose (SMPG) profiles. The following endpoints will be derived:

- 7-point profiles at week 54 and week 80
- Change in postprandial glucose (PPG)/prandial increment (breakfast, lunch, dinner and average over the three meals) from baseline to week 54 and week 80
- Change in mean of 7-point profiles from baseline to week 54 and week 80
- Before breakfast SMPG at week 54 and week 80
- Change in patient reported outcome (PRO) scores (SF36, Experience of Treatment Benefits and Barriers, Diabetes Treatment Satisfaction Questionnaire (DTSQ)) from baseline to week 54 and week 80

\* Key supportive secondary endpoint prospectively selected for disclosure (e.g. clinicaltrials.gov and EudraCT)

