## 2.1 Sample size calculation

This is a phase 2 trial and the first Novo Nordisk trial of NNC0114-0006 in subjects with newly diagnosed T1DM. Therefore the knowledge on treatment effects and on the standard deviation of the primary endpoint is limited.

The statistical power calculations have been done under the following assumptions

- The primary endpoint is  $AUC_{0-4h}$  for a MMTT stimulated C-peptide concentration-time curve at week 54 relative to baseline, i.e.  $AUC_{0-4h, C-peptide, 54w} / AUC_{0-4h, C-peptide, baseline}$ . The primary endpoint will be log-transformed in the statistical analysis and this will be denoted  $\ln(AUC_{0-4h, C-peptide, \Delta 54w})$ . Thus,  $AUC_{0-4h, C-peptide, \Delta 54w}$  is the proportion of  $AUC_{C-peptide}$  that is preserved after 54 weeks relative to the level at baseline. E.g. a reduction of  $AUC_{C-peptide}$  of 35% corresponds to a preservation of 65% and value of the  $\ln(AUC_{0-4h, C-peptide, \Delta 54w})$  is  $\ln(0.65) = -0.431$ .
- The residual standard deviation of  $\ln(AUC_{0-4h, C-peptide, \Delta 54w})$  in the model described above may depend on the treatment. Based on the results of Herold et al. the standard deviation is assumed to be 1 in the placebo group and 0.5 in the group treated with NNC0114-0006 in combination with liraglutide.
- The expected preservation in the placebo treated patients is 65%, based on the results of Herold et al. who found a mean of 70% decline in  $AUC_{C-peptide}$  over a 24-months period. Assuming a linear decline, the mean 12-months decline would be 35%, i.e. a preservation of 65%. The statistical power calculations have been done assuming three levels of treatment effects for NNC0114-0006 in combination with liraglutide; a preservation of 85% and 95% and 98%, respectively.

[Table 2-1](#) shows the statistical power for the test of no treatment effect if the true mean preservation is 85%, 95% or 98% in the group treated with NNC0114-0006 in combination with liraglutide and 65% in the placebo group when the numbers of completers are 40, 60 or 80, respectively using a two-sided test and 5% level of significance. The rows corresponding to the chosen number of (completing) subjects are highlighted.

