**Table 2–1 Power calculations**

True treatment effect (preservation)	N (completers per group)	Statistical power
85%	40	0.320
85%	60	0.451
85%	80	0.566
95%	40	0.561
95%	60	0.740
95%	80	0.854
98%	40	0.628
98%	60	0.804
98%	80	0.903

Assuming a preservation of 98% and a SD of 0.5 for NNC0114-0006 in combination with liraglutide and a preservation of 65% and a SD of 1 for placebo, then the power will be 80.4% with 60 subjects completing the trial in each of the two treatment arms.

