### 2.3 Primary endpoint

The primary endpoint is  $AUC_{0-4h}$  for a MMTT stimulated C-peptide concentration-time curve at week 54 relative to baseline:  $AUC_{0-4h, C-peptide, 54w} / AUC_{0-4h, C-peptide, baseline}$ .

The  $AUC_{0-4h}$  for MMTT stimulated C-peptide is derived at baseline and at 12, 24, 36, and 54 weeks and is denoted  $AUC_{0-4h, C-peptide, t}$ , where  $t$  is the time of the assessment. Thus,  $t=54$  weeks corresponds to the primary endpoint.

More specifically,  $AUC_{0-4h, C-peptide, t}$  at time 't' will be determined as the area from 0 to 4 hours under the C-peptide concentration profile after a MMTT using the trapezoidal method based on observed concentration values and actual measurement times. If the MMTT is stopped before 4 hours due to hyperglycaemia or hypoglycaemia, the last measured C-peptide concentration will be carried forward for calculation of the primary endpoint. If the MMTT is stopped before 4 hours it will most likely be due to hyperglycaemia as hypoglycaemia is not expected when a high amount of carbohydrates are ingested. Using last observation carried forward (LOCF) will result in an overestimated AUC since the C-peptide response is expected to be at the maximum level during hyperglycaemia. Furthermore, the risk of hyperglycaemia during MMTT will be higher in the placebo group if the active treatments have an effect on beta-cell preservation. Thus, LOCF is considered as a conservative approach. In case the MMTT is stopped before 4 hours for reasons that are not due to hyperglycaemia or hypoglycaemia, the remaining C-peptide concentrations will be set to  $lloq/2$ .

Let  $y_{it}$  denote the value of  $AUC_{0-4h, C-peptide, \Delta t}$  evaluated relative to baseline at time  $t$  for subject  $i$ , i.e.

$$y_{it} = \text{AUC}_{0-4h, \text{ C-peptide}, \Delta t} = \text{AUC}_{0-4h, \text{ C-peptide}, t} / \text{AUC}_{0-4h, \text{ C-peptide}, \text{ baseline}}$$

log of  $y_{it}$  will be analysed using an (MMRM) including all available assessments over time with treatment, stratum and sex as factors and  $\ln(\text{AUC}_{0-4h, \text{ C-peptide}, \text{ baseline}})$  and age at baseline as covariates (see [Table 2-2](#)). The interaction between all variables and visit (week) will be included in the model as fixed effects.

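### Carry-forward after a stopped meal test is justified for C-peptide only, yet it also governs plasma glucose AUC0-4h, where the same reasoning would favour the active arms and no check is planned

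*SAP*

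**What the plan says.** SAP 2.3 (as protocol 17.3) sets the rule. If a meal test ends before 4 hours because of hyper- or hypoglycaemia, the last measured C-peptide value is held to 4 hours. Two reasons are given. First, the AUC will be too high, because C-peptide should be at its maximum during hyperglycaemia. Second, "the risk of hyperglycaemia during MMTT will be higher in the placebo group if the active treatments have an effect on beta-cell preservation". The conclusion is: "Thus, LOCF is considered as a conservative approach". For stops of any other kind, SAP 2.3 sets the remaining C-peptide values to lloq/2.

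SAP 2.4.1.1, on the other endpoints from the mixed meal tolerance test, covers the C-peptide and plasma glucose curves together: "The AUC endpoints will be derived using the same approach as described for the primary endpoint". Protocol 17.4.1.1 has the same sentence. The glucose endpoints are AUC0-4h and AUC0-2h "for MMTT stimulated plasma glucose concentration time curve at week 54 and week 80 relative to baseline" (SAP 1.1.2.2). They are not starred as key. Neither document gives glucose a rule of its own, and the list of changes in SAP section 3 makes no exception.

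Two analyses in SAP 2.3 remove results from stopped tests and from profiles with imputed values. Their heading limits them to the primary endpoint.

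**The concern.** The conservative argument needs three things: a carried value that is too high, more stops on placebo, and an outcome for which higher is better. The third holds for C-peptide and fails for glucose. There is also selection. Under protocol 8.3.1 a hyperglycaemic stop requires glucose above 16.7 mmol/l together with raised ketones, so the glucose value carried forward has been picked for being high. At stake is whether a week-54 or week-80 difference in glucose AUC0-4h could come partly from the imputation, with no planned analysis to show how much.

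**Working it through.** **The plan's own figures.** The plan gives no stop rate, stop time or bias estimate, so there is no figure on this point to reproduce. The nearest one is the power for the primary endpoint. With difference ln(0.98/0.65) = 0.411, SDs 1 and 0.5 and 60 completers per arm, SE = sqrt((1 + 0.25)/60) = 0.144. Power is 0.812 by the normal approximation and 0.803 by a Welch t test, against the stated 0.804. This point does not touch that figure.

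**Direction, on the SAP's premises.**

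| | C-peptide AUC | Glucose AUC |
|---|---|---|
| Carried value too high | overstated | overstated |
| Arm with more stops | placebo | placebo |
| Higher value means | better | worse |
| Effect on the comparison | against active | in favour of active |

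**Size for one stopped test.** Method: trapezoidal AUC0-4h on the protocol 8.3.1 sampling times from 0 to 240 min, with and without carry-forward. The profiles are assumptions, in mmol/l at 0, 15, 30, 60, 90, 120, 150, 180, 210 and 240 min.

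- Falling: 8, 9.5, 12, 15.5, 17.5, 17, 16, 14.5, 13, 11.5. Full AUC0-4h = 57.5. Stop at 90 min: 20.0 + 2.5 × 17.5 = 63.75, or +10.9%. Stop at 120 min: 28.625 + 2 × 17 = 62.625, or +8.9%.
- Plateau at 17.5 from 90 min: no change.
- Still rising: 8, 9.5, 12, 15.5, 17.5, 18.5, 19.5, 20, 20, 19.5. Full AUC0-4h = 68.25. Stop at 90 min: 63.75, or -6.6%. Stop at 120 min: 29.0 + 2 × 18.5 = 66.0, or -3.3%.

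Piecewise-linear curves agree:

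- 7.5 to 19 at 90 min, then to 13: +12.5% for a stop at 90 min.
- 8.5 to 20 at 120 min, then to 16: -3.8% for a stop at 90 min and +6.2% at 120 min.

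With C-peptide curves of similar assumed shape, a stop at 90 min gives +15.3% if falling and -5.2% if rising. On these shapes one carry-forward rule is not conservative for both analytes at once.

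**AUC0-2h.** A stop at 120 min or later cannot change it. For stops at 90 min with glucose above 16.7 mmol/l, the profiles above give -2.5% to +1.0%. An example is 27.78/28.5 - 1 = -2.5% for the curve from 8.5 to 20.

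**Shift in the arm ratio.** Let b be the relative error in a stopped test's AUC0-4h, and p_A and p_P the proportions of tests stopped. With unstopped baseline tests and the same b in both arms, the active/placebo geometric mean ratio moves by exp[(p_A - p_P) × ln(1 + b)] - 1.

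| Assumed stops, placebo / active | Falling (b = +8.9% to +10.9%) | Still rising (b = -3.3% to -6.6%) |
|---|---|---|
| 5% / 2% | -0.3% | +0.1% to +0.2% |
| 10% / 5% | -0.4% to -0.5% | +0.2% to +0.3% |
| 20% / 5% | -1.3% to -1.5% | +0.5% to +1.0% |
| 30% / 10% | -1.7% to -2.0% | +0.7% to +1.4% |

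Negative values favour active.

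**lloq/2.** That rule names C-peptide, but the cross-reference could be read to include glucose. With an assumed lloq/2 of 0.05 to 0.5 mmol/l from 120 min onward, after a stop at 90 min on the falling profile, AUC0-4h would be 24.5 to 25.5 instead of 57.5. That is a fall of 56% to 57%.

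**The case against.** The strongest reply has four parts.

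- **The sign is not established.** It depends on glucose falling after the stop. Insulin is restricted before the test (protocol 8.3.1), so a late rise is plausible. This stands. A reader might infer that the glucose results are bound to flatter the active arms, but the documents do not settle the shape of the curve after a stop.
- **The effect is small and the endpoints are minor.** Pre-meal glucose must be at most 9.0 mmol/l, a hyperglycaemic stop also needs raised ketones, and these endpoints are supportive in a proof-of-principle trial. The 2% shift needs 30% of placebo tests to be stopped. This also stands, and it limits the weight of the point.
- **Carrying glucose forward is not spelled out.** The sentence in SAP 2.3 names C-peptide and the primary endpoint. That is correct, but SAP 2.4.1.1 refers to the same approach straight after naming the glucose curves. On any other reading, stopped glucose tests have no rule at all.
- **There is some protection already.** SAP 2.2 has treatment-phase C-peptide and glucose profiles examined before the interim lock, leaves endpoints uncalculated where important samples are missing, and allows further sensitivity analyses. This helps, but it is discretionary and does not commit to any analysis of stopped glucose tests.

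A low value carried forward after a hypoglycaemic stop would lower that arm's AUC. The SAP does not expect such stops and does not say in which arm they would fall.

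**Conclusion.** The point holds in a limited form. The carry-forward rule reaches the plasma glucose AUC endpoints by cross-reference, its justification does not, and no exclusion analysis is planned for them. On the SAP's premises the rule favours active for AUC0-4h; if glucose was still rising it works against active. Over the assumed profiles and stop rates the ratio shifts by about 2% or less in either direction.

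Three stronger readings are not supported:

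- That AUC0-2h shares the problem to a similar degree. Most stops change it little or not at all.
- That the primary endpoint is exposed without a check. An early stop could indeed understate C-peptide AUC, but SAP 2.3 already plans both exclusion analyses for that endpoint.
- That the SAP calls carry-forward conservative for glucose. The word appears only in the argument about C-peptide.

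**What to change.** In SAP 2.4.1.1:

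1. State that the conservative rationale in SAP 2.3 applies to C-peptide and does not extend to plasma glucose.
2. State that the lloq/2 rule is not applied to glucose.
3. Extend the two existing exclusion analyses (tests stopped for hyper- or hypoglycaemia, and profiles with imputed values) to glucose AUC0-4h at weeks 54 and 80. Report them beside the carry-forward result as a bracket.

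Leave the primary endpoint derivation unchanged. A matched interval (AUC to the stop time over baseline AUC to the same time) is tempting but should not be used. It would redefine the primary endpoint, and it errs when the peak moves, which is plausible because liraglutide delays gastric emptying (protocol 3.1). If a C-peptide curve of 0.3 to 0.7 to 0.5 nmol/l moves its peak from 90 to 150 min, the matched ratio is wrong by -8% to -12% for stops at 60 to 120 min. If the glucose curve 7.5 to 19 to 13 moves its peak from 90 to 120 min, a stop at 120 min gives -7%.

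The cost is a few sentences and a little more analysis. Exclusion drops high-glucose tests and may err in the other direction, so it should sit beside the carry-forward result and not replace it.

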##### **Insulin dose**

The total daily insulin dose will be derived as the average of the doses per kg body weight reported on the three days prior to visit 3, 63 and 89.

The endpoints will be analysed using normal linear regression model for the endpoint with treatment, stratum and sex as fixed factors and age and baseline value as covariates. Treatment means (LSMeans) and treatment differences will be presented with 95% CIs. The analysis will not account for missing data.

The endpoints will be summarised using descriptive statistics and presented graphically.

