# 6 Trial population

# 6.1 Number of subjects

Number of subjects planned to be screened: 600

Number of subjects planned to be randomised: 304

Maximum number of subjects to be randomised: 314

Number of subjects expected to complete the trial (defined as reaching primary endpoint): 240

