# 8.3.5 Insulin doses

Subjects will be instructed in how to record the insulin doses in the e-diaries. Each record should include date, time point (e.g. before breakfast, before lunch etc.), value, units and type (basal or bolus) of insulin.

Insulin doses will be collected on a daily basis to allow optimal insulin titration.

If a subjects reports an actual bolus insulin dose that deviates from the prescribed bolus insulin dose the subject will be asked to report a reason for this deviation in the e-diary.

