# **11** Randomisation procedure and breaking of blinded codes

This trial is double-blind. A randomisation session will be carried out for all subjects using the IV/WRS. At the randomisation visit (Visit 3) subjects meeting all inclusion and randomisation criteria and none of the exclusion criteria will be centrally randomised to one of the 4 parallel treatment groups in a 1:1:1:1 manner to:

- NNC0114-0006 C 100 mg/ml 12 mg/kg i.v. every 6 weeks and liraglutide 1.8 mg s.c. daily
- NNC0114-0006 C 100 mg/ml 12 mg/kg i.v. every 6 weeks and liraglutide placebo 0 mg s.c. daily
- NNC0114-0006 C 0 mg/ml i.v. every 6 weeks and liraglutide 1.8 mg s.c. daily
- NNC0114-0006 C 0 mg/ml i.v. every 6 weeks and liraglutide placebo 0 mg s.c. daily

The randomisation will be stratified according to non-fasting C-peptide levels:

- non-fasting C-peptide  $\geq 0.2$  nmol/l to  $\leq 0.6$  nmol/l
- non-fasting C-peptide >0.6 nmol/l

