#### Insulin dose

The total daily insulin dose will be derived as the average of the doses reported on the three days prior to the visit.

The endpoints will be analysed using a similar model as applied for the primary endpoint except that the dose at baseline will be included as a covariate. The analysis will be made on the original scale (i.e. without log-transformation). Consequently, treatment means (LSMeans) and treatment differences will be presented with 95% CIs.

The endpoints will be summarised using descriptive statistics and presented graphically.

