# 4 Data collection

The following data should be available for Novo Nordisk's Insulin Titration Group for all subjects within 24 hours (on weekdays) after a site visit/phone contact:

- SMPG values
- Carbohydrate intake per meal (CHO-counting subjects only)
- Date and insulin doses taken (daily)
- New insulin doses prescribed after titration
- Reason for deviation between the recommended and the prescribed basal insulin dose
- Reason for deviation between the recommended and actual bolus insulin doses
- Hypoglycaemic episodes

Furthermore the investigator should provide the following from the CHO-counting subjects:

- I:CHO ratio per meal (initial and any changes)
- Plasma glucose correction factor per meal (initial and any changes)

CONFIDENTIAL

Date: Version: Status: Page: 07 May 2015 **Novo Nordisk** 2.0 Final 10 of 11

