- The description of the stratification variable has been updated from non-fasting C-peptide measurement at screening to non-fasting peak C-peptide measurement during MMTT at Visit 2 in alignment with protocol amendment 2.
- In the analysis of the primary endpoint, it has been deleted, that the variance-covariance matrix may depend on treatment, if an assumption of equal variance-covariance matrix between treatments turns out not to be reasonable. Instead it has been included that a sensitivity analysis where the variance-covariance matrix depends on treatment will be added if an assumption of equal variance-covariance matrix between treatments turns out not to be reasonable.

- Update of the first sensitivity analysis to specify that it is the endpoints calculated from MMTT stopped before 4 hours due to hyperglycaemia or hypoglycaemia that are excluded from the analysis, and not all the data for that subject.
- Sensitivity analysis added where endpoints calculated from MMTT profile that includes imputed values is excluded.
- Sensitivity analysis added where endpoints calculated from the MMTT, where the date of the MMTT is more than one day after the last liraglutide dosing is excluded.
- In the analysis exploring the effect of the different biomarkers on primary endpoint, the description of the analysis for categorical biomarkers has been deleted, as all biomarkers are continuous.
- In the exploratory analysis that investigates a potential effect of the concentration of liraglutide on the primary endpoint, it has been specified that the liraglutide concentration should be measured at the date corresponding to the MMTT, and not just the visit corresponding to the MMTT. The specification is done as the MMTT can be re-scheduled within 1-10 days.
- In alignment with the endpoint description in Section [1.1.2.2](#), it is specified that the endpoint for total daily insulin dose is derived per kg body weight.
- As only the insulin doses prior to visit 3, 63 and 89 will be transferred from the eDiary (as per the trial data handling plan), the description of the endpoints has been updated, and the statistical analysis has been changed from a MMRM to a normal regression model:
  - The total daily insulin dose will be derived as the average of the doses reported on the three days prior to visit 3, 63 and 89.

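### The key insulin-dose endpoint moves from the protocol's repeated-measures model to a single-visit regression with no missing-data handling, for a data-transfer reason only

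*SAP*

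**What the plan says.** SAP 1.1.2.2 lists change in total daily insulin dose per kg (three-day average) to weeks 54 and 80 with the asterisk for key supportive endpoints selected for disclosure.

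The protocol's analysis (17.4.1.1, Insulin dose) is: "The endpoints will be analysed using a similar model as applied for the primary endpoint", with baseline dose as covariate and no log transformation.

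SAP 2.4.1.1 replaces this with a normal linear regression on treatment, stratum, sex, age and baseline dose, using only the windows before Visits 3, 63 and 89, and adds: "The analysis will not account for missing data". SAP section 3 gives the reason: "As only the insulin doses prior to visit 3, 63 and 89 will be transferred from the eDiary", citing the trial data handling plan. It lists the change among those made before the randomisation code break.

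On the data themselves, Protocol 8.3.5 says: "Insulin doses will be collected on a daily basis to allow optimal insulin titration". Under Protocol 13.3, e-diary entries pass automatically to a database and go on to the sponsor's trial database at intervals. Appendix A, section 4, requires daily doses to be available to the sponsor's titration group within 24 hours of each contact on weekdays.

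**The concern.** The change follows from how much e-diary data is extracted, not from what is measured. The contrast with eGFR is useful. Its repeated-measures model was also dropped, but because eGFR is assessed only at Visits 1, 63 and 89, so no interim values exist. For insulin dose they do.

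All arms are titrated to the same glucose targets, so insulin dose and HbA1c need to be read together. HbA1c keeps the repeated-measures model (SAP 2.4.1.1). The two results would therefore rest on different missing-data assumptions and different contributing subjects.

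Some mandatory withdrawal criteria in Protocol 6.6 could plausibly go with insulin need, such as hyperglycaemia with ketosis that poses a safety concern. If such withdrawals are related to dose during treatment, and differently so by arm, a comparison of those who remain can be biased.

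**Working it through.** **1. The plan's own figures.** Protocol 6.1: "Number of subjects planned to be randomised: 304" and "Number of subjects expected to complete the trial (defined as reaching primary endpoint): 240". With four equal arms, that is 304/4 = 76 randomised and 240/4 = 60 completing per arm. Expected loss to week 54 is (304 − 240)/304 = 64/304 = 21.05%.

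The 60 per arm is the basis of the stated 80.4% power in SAP 2.1. The difference is ln(0.98/0.65) = 0.411 and the standard error is √((1² + 0.5²)/60) = 0.144. A noncentral t calculation with Satterthwaite degrees of freedom gives 0.803, so the figure reproduces. It concerns the primary endpoint. No SD or power is given for insulin dose.

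**2. Whether 21% is the missing fraction.** Withdrawal is final and subjects are not replaced, so loss at week 80 is at least as large. Against this, Protocol 8.1.7 asks investigators to aim for Visit 63-type procedures when a subject withdraws during treatment, and Protocol 18.3 retains such data for the report. The SAP does not say whether a dose from that visit counts as the Visit 63 value, or whether its window is transferred. So 21% is an upper figure under the planned dropout.

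**3. What the regression assumes.** It is unbiased if, given treatment, baseline dose, stratum, sex and age, being missing is unrelated to the later dose. A repeated-measures model relaxes this: missingness may also depend on doses already observed.

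**4. When the two differ (illustration only).** The documents give no SD, correlation or dropout mechanism for insulin dose, so all of the following is assumed:
- two arms of 76, outcome SD 1, true week-54 difference −0.40 SD
- visits at weeks 12, 24, 36 and 54, with adjacent-visit correlation 0.6, 0.8 or 0.9
- about 21% monotone dropout
- where dropout is dose-related, its log-odds change by 1 per SD of the last dose.

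Each cell gives results for the three correlations in turn.

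| Dropout | Complete-case estimate | Repeated-measures estimate | SE, complete-case / repeated-measures |
|---|---|---|---|
| (a) unrelated to dose | −0.399, −0.406, −0.403 | −0.399, −0.407, −0.402 | 0.182/0.179, 0.173/0.169, 0.137/0.132 |
| (b) last dose, same direction in both arms | −0.394, −0.393, −0.394 | −0.406, −0.405, −0.402 | 0.180/0.179, 0.164/0.160, 0.138/0.134 |
| (c) last dose, opposite directions by arm | −0.277, −0.252, −0.283 | −0.402, −0.397, −0.398 | 0.176/0.176, 0.166/0.166, 0.136/0.132 |

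In (a) and (b) the analyses all but agree. In (c) the complete-case estimate shrinks by 1 − 0.283/0.40 = 29% to 1 − 0.252/0.40 = 37%. The precision gain in (a) is 1 − 0.179/0.182 = 1.6% to 1 − 0.132/0.137 = 3.6% of the SE. For scale, falling from 76 to 60 per arm raises the SE by √(76/60) = 1.125, most of which no model recovers.

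**The case against.** The strongest reply is that the choice is open and tolerable. It was declared with a reason before code break. The regression adjusts for baseline dose and the main prognostic factors. Unequal dropout alone does not bias it. The repeated-measures model needs missing-at-random too. The case that separates the two analyses, dose-dependent dropout in opposite directions by arm, is not one that the documents predict. This is also one supportive endpoint among many in a proof-of-principle trial. All of that stands, and it limits the point to a modest one.

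It also rules out several stronger readings that a reader might infer:
- *That every withdrawn subject has unused interim doses.* Those leaving before week 12 have none at the proposed visits, and the protocol itself anticipates gaps in the diary.
- *That withdrawal is generally driven by insulin need.* Protocol 6.6 has 14 mandatory criteria. Most, such as raised calcitonin, viral infection, pregnancy, missed infusions and eligibility violations, have no stated link to it.
- *That the bias can be put in U/kg.* That needs dropout rates by arm and the dose gap between dropouts and completers, and the documents give neither.
- *That the data are already in the analysis database.* The titration group is described as not otherwise involved in trial conduct (Protocol 14.2), and the data handling plan is a separate document. Protocol 13.3 makes transfer plausible; it does not prove it easy.

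What the reply does not supply is a scientific reason for dropping the protocol's model.

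**Conclusion.** The point holds as a cheap improvement. A key endpoint loses the protocol's model for an administrative reason, and its missing-data assumption becomes stricter than the one kept for HbA1c. The exposure is up to about 21% of subjects at week 54 and at least as many at week 80, assuming dropout as planned. It could be smaller if withdrawal-visit doses are used. Whether bias follows depends on dropout being tied to on-treatment insulin need differently by arm. Its size and direction cannot be derived from the documents, and the illustration above is not an estimate for this trial. The argument rests on possible bias, since precision would hardly change.

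A reader might also infer that the change was made with knowledge of results. SAP section 3 dates it before the code break, and nothing in the documents contradicts that.

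**What to change.** Transfer the three-day dose windows before the mixed-meal visits at weeks 12, 24, 36 and 65 as well. Daily doses and body weight are already collected there, so dose per kg can be derived. Restore the protocol's repeated-measures model on the full analysis set, so that insulin dose and HbA1c share one missing-data assumption.

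If the transfer is not feasible, use multiple imputation based on treatment, baseline dose and interim HbA1c, body weight and C-peptide AUC. Model Visits 63 and 89 jointly, so that week-54 doses inform week 80.

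In either case, state in the SAP whether a dose recorded at a withdrawal visit counts as the Visit 63 or Visit 89 value, and whether its window is transferred.

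Cost: one more e-diary extract with its cleaning, or the imputation work, plus an update to the data handling plan and one SAP paragraph. There is no added burden for subjects.
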